4. ENDPOINTS

4.1. Primary endpoint

- 1) Occurrence of *H. influenzae*, *S. pneumoniae*, *M. catarrhalis* and other bacteria in BAL fluid samples of subjects aged ≥ 6 months to < 6 years visiting the hospital with suspected chronic LRTIs and an indication for BAL
 - *H. influenzae*, *S. pneumoniae* and *M. catarrhalis* confirmed by bacterial load $>10^4$ cfu/mL if present alone or 10^5 cfu/mL if present as co-infection.

4.2. Secondary endpoints

In a hospital setting and among subjects aged ≥ 6 months to < 6 years with suspected chronic LRTIs and an indication for BAL:

- 1) Bacterial load of *H. influenzae*, *S. pneumoniae* and *M. catarrhalis* in the BAL fluid as determined by quantitative culture and PCR.
- 2) Description of other bacterial pathogens in the BAL fluid as determined by qualitative culture.
- 3) Bacterial load of *H. influenzae*, *S. pneumoniae* and *M. catarrhalis* in nasopharyngeal swab samples as determined by quantitative culture and PCR.
- 4) Description of other bacterial pathogens in nasopharyngeal swab samples as determined by qualitative culture.
- 5) Occurrence of *H. influenzae*, *S. pneumoniae*, *M. catarrhalis* and other pathogens detected by culture in the nasopharyngeal swab samples.
- 6) Occurrence of *H. influenzae* and *S. pneumoniae* serotypes identified from BAL fluid samples and nasopharyngeal swab samples.
- 7) Occurrence of *H. influenzae*, *S. pneumoniae* and *M. catarrhalis* minimum inhibitory concentration (MIC) values identified from BAL fluid and nasopharyngeal swab samples.
- 8) Demographic characteristics (age, gender, etc), clinical characteristics (including medical history, LRTI symptoms, treatment history, vaccination status, etc),

radiological evidence and laboratory results (including white blood cell counts, CRP level and erythrocyte sedimentation rate, if available).

5. STUDY POPULATION

5.1. Screened cohort

The screened cohort will include all subjects who visit the hospital with suspected chronic LRTIs and have an indication for BAL. All the information (anonymised) for these subjects will be collected in the aggregated logbook.

5.2. Total cohort

The total cohort will include all enrolled subjects.

5.3. According-To-Protocol cohort

The ATP cohort will include all evaluable subjects (i.e. those meeting all eligibility criteria and complying with the procedures defined in the protocol during the study) with BAL fluid sampling and/ or nasopharyngeal swab sampling results available.

The list of applicable elimination codes for each cohort can be found in the study specific form FORM-BIO-CLIN-9004-05 Criteria for eliminating subjects from the analyses.

Cohort	Elimination codes	Eli Type
Total cohort	NA	MA
ATP cohort	900, 2010, 2040, 2050, 2060, 2100, 2120, 2500	MA

6. STATISTICAL METHODS

All statistical analyses will be done using SAS version 9.2 or later.

Continuous variables will be described using the mean, standard deviation, median, minimum and maximum. Categorical variables will be described using frequency tables (absolute numbers and percentages for levels of each variable, excluding missing values). For continuous and categorical variables, the number of missing observations will be recorded.

All the analyses will be performed on the ATP cohort. If the percentage of subjects from the Total effective cohort with serological results excluded from the ATP cohort is more

than 5%, a second analysis of the demography and the primary objective based on the Total effective cohort will be performed to support the ATP analysis.

6.1. Analysis of demographics/ baseline characteristics

Demographic, clinical and microbiological characteristics of subjects will be described using percentages for categorical variables and mean (standard deviation) or median (min-max) for continuous variables. The same variables will be presented descriptively, overall and by microbiological results.

6.1.1. Demographic characteristics

The number of screened and enrolled subjects as well as the number excluded from ATP analyses will be presented.

Demographic characteristics (age in months, gender, weight in kg, height in cm and BMI categories, such as extreme obesity, obesity, overweight normal, thinness and marked thinness (details see section 7.1))will be summarised using descriptive statistics (for all non-missing observations) overall and by center. Height and weight will also be tabulated by age groups.

6.1.2. Clinical characteristics

The following tables will be generated for the following endpoints:

- Chronic LRTI symptoms
 - The bronchoscopy details will be presented: the percentage of subjects for each indication (cough, wheezing, pathologic auscultation, infiltrates/atelectasis) as well as for each fibro-bronchoscopy indication will be tabulated overall and by center.
 - The percentage of subjects presenting respiratory or otitis media pre-existing conditions will be tabulated.
 - Number of previous episodes reported by subject within the last 12 months will be tabulated as well as the description of current cough.
- Medical history:
 - The percentage of subjects reporting any disease/conditions in the general medical history will be tabulated overall and by center. Summary of listed conditions will be tabulated overall and by center.

Study alias & e-track number(s): EPI-STREP-064 BOD ES (115813)

- Vaccination history (vaccination against Pneumococcal, *Haemophilus influenzae* B and Influenza) will be tabulated and percentage of pneumococcal vaccine administered (prevenar7, prevenar13, pneumovax or synflorix) presented.
- Feeding practices and day care practice:
 - If the child has ever been breastfed or not, the number of other children living in the same household for more than 3 days a week, and if the child is at a day care center and/or school at least 2 days a week or not, will be presented in a frequency table;
- Environmental exposure and smoking environment
 - The percentage of children living within 1 km of major pollution source and the source of the pollution (Major roadway, Highway, Area where trucks/vehicles idle, major industry area with smokestacks and other category) will be tabulated.
 - The percentage of children exposed more than 3 days a week to indoor cigarette smoke will also be tabulated.

6.1.3. Antibiotic therapy and other treatments

The percentage of subjects that took antibiotics within the 6 months prior to the visit will be tabulated. Trade/Generic name of Antibiotics will be tabulated. The same tables will be presented for other medications taken for this condition within the past 6 months.

6.1.4. Physical examination

Vital signs such as temperature, heart rate, blood pressure and respiratory rate will be presented.

6.1.5. Radiological results

The percentage of subjects that had a Chest X-Ray (CXR) done will be presented.

The findings from the CXR will be presented as frequency table stratified overall and by center. The percentage of subjects with an abnormal result from the CXR which was relevant to the decision to collect BAL sample will be presented.

6.1.6. Laboratory results: WBC, CRP, ESR, microbiological culture, antibiotic resistance test

The following results of laboratory tests in subjects for which they are available will be presented:

Statistical Analysis Plan

Study alias & e-track number(s): EPI-STREP-064 BOD ES (115813)

- Mean, Median and range of White Cell count level along with standard deviation will be presented overall and by center for subjects for whom blood sample is available and white cell count analyzed. The same will also be presented by age group.
- Mean, Median and range of CRP level along with standard deviation will be presented for subjects for whom blood sample is available and CRP test was done. The same will also be presented by age group.
- CRP levels (see Table 1 below) will also be presented in groups overall and stratified by age group.

Table 1 CRP categories for the analysis

CRP	1	<40 mg/L	CRP <40 mg/L
	2	>=40 - <80 mg/L	40 mg/L <=CRP <80 mg/L
	3	>=80 - <120 mg/L	80 mg/L <=CRP <120 mg/L
	4	>=120 mg/L	CRP >=120 mg/L

- Mean, Median and range of Erythrocyte sedimentation rate (ESR) level along with standard deviation will be presented overall and by center for subjects for whom blood sample is available and ESR analyzed. The same will also be presented by age group

6.1.7. BAL fluid samples and nasopharyngeal swab

The percentage of subjects for whom BAL fluid sample was taken will be presented overall and by center. The same will be tabulated for nasopharyngeal swab samples taken.

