3.1. Discussion of study design

A cross-sectional study design is the simplest approach to describe the burden of disease, *i.e.* bacterial aetiology of chronic LRTI symptoms. BAL is routinely performed for diagnosis of infection in children with such chronic symptoms, and it is unlikely to be performed repeatedly for otherwise healthy children. Thus, extended follow-up would not be possible.

Considering the invasive nature of the BAL fluid sampling procedure, it has been decided to enrol only those subjects with suspected chronic LRTIs who have BAL procedure indicated by their clinician as part of the local routine diagnostic procedure. This should facilitate subject recruitment and increase participation rates. Nasopharyngeal swabs may not be systematically collected in routine practice. However, since the patient will be under sedation to undergo BAL, he/she will not be subject to additional discomfort or risk due to the swabbing procedure. Thus, it is not expected to affect the willingness of the parent(s)/ LAR(s) to allow their child's participation in this study.

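### The sample-collection table in SAP 6.1.7 falls on the ATP cohort, so enrolled children with neither a BAL nor a swab result are left out of the completeness percentage

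*SAP*

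**What the plan says.** SAP 6.1.7 has two sentences: "The percentage of subjects for whom BAL fluid sample was taken will be presented overall and by center", and "The same will be tabulated for nasopharyngeal swab samples taken". Neither names a cohort.

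SAP 6 supplies the default: "All the analyses will be performed on the ATP cohort". SAP 5.3 limits that cohort to eligible, compliant subjects "with BAL fluid sampling and/ or nasopharyngeal swab sampling results available". The wider cohort is defined in SAP 5.2: "The total cohort will include all enrolled subjects".

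SAP 6 also provides for a supportive analysis. Its trigger reads "If the percentage of subjects from the Total effective cohort with serological results excluded from the ATP cohort is more" than 5%, and what then follows is "a second analysis of the demography and the primary objective based on the Total effective cohort will be performed to support the ATP analysis". SAP 6.1.1 separately reports how many subjects were screened, enrolled and excluded from ATP.

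**The concern.** A table of who was sampled should start from everyone who could have been sampled. Here the denominator depends on the outcome being described, because having a result from at least one sample is a condition of entry.

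Enrolled children with no sample can arise. Consent precedes every other study procedure (Protocol 5.5.2.2), and enrolment is dated at signature of the consent form (Protocol 7.4, SAP 7.1). A child is therefore enrolled before anything is collected. Protocol 3.1 justifies the swab "since the patient will be under sedation to undergo BAL", so a bronchoscopy that does not go ahead could plausibly cost both samples.

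What is at stake is how a reader judges selection. The primary proportions in SAP 6.2 use only children with a BAL result. The share of enrolled children who were sampled, and whether any centre falls short, tells the reader how selected that group is. SAP 6.1.7 is the only by-centre sampling table the SAP text promises.

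**Working it through.** **The plan's own figures.** The documents state no figure for sampling completeness. Their only computed figures are the exact 95% intervals in Protocol 7.2 for 150 subjects. These reproduce with the Clopper-Pearson method: 17/150 = 11.3% gives 6.74 to 17.52 (stated 6.7 to 17.5), and 50/150 = 33.3% gives 25.86 to 41.48 (stated 25.9 to 41.5). They do not bear on this point beyond fixing the planned size.

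**Inputs.**
- N = enrolled children. Protocol 4.1 plans at least 150, in at least 5 hospitals; 150/5 = 30 per centre is an assumed average.
- m = enrolled children excluded from ATP because neither sample gave a result (assumed).
- t = those among the m in whom BAL was nevertheless taken (assumed).
- s = children in ATP through a swab result alone, with no BAL taken (assumed).
- ATP exclusions for other reasons are set aside.

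**Formulas for the percentage with BAL taken.**
- Total cohort: (N − s − m + t)/N
- ATP cohort: (N − s − m)/(N − m)

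The ATP figure is the higher one only when t/m is below the Total-cohort proportion. The two extremes for the difference, ATP minus Total, are:
- t = 0 (no BAL taken in any of the m): m(N − s − m)/[N(N − m)], which equals m/N when s = 0.
- t = m (BAL taken in all of them, no result): −sm/[N(N − m)], which is zero or slightly negative.

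**Results for N = 150.**

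| s | m | t | Total cohort | ATP cohort | Difference (points) |
|---|---|---|---|---|---|
| 0 | 3 | 0 | 147/150 = 98.0% | 147/147 = 100% | +2.0 |
| 0 | 8 | 0 | 142/150 = 94.7% | 142/142 = 100% | +5.3 |
| 0 | 15 | 0 | 135/150 = 90.0% | 135/135 = 100% | +10.0 |
| 5 | 3 | 0 | 142/150 = 94.7% | 142/147 = 96.6% | +1.9 |
| 5 | 8 | 0 | 137/150 = 91.3% | 137/142 = 96.5% | +5.2 |
| 5 | 15 | 0 | 130/150 = 86.7% | 130/135 = 96.3% | +9.6 |
| 0 | 15 | 15 | 150/150 = 100% | 135/135 = 100% | 0.0 |
| 5 | 15 | 15 | 145/150 = 96.7% | 130/135 = 96.3% | −0.4 |

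**One assumed centre of 30, s = 0, t = 0.** With m = 1, 3 or 6, the Total-cohort figure is 96.7%, 90.0% or 80.0%. The ATP figure is 100% each time.

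**Does another part of the SAP recover these children?** The supportive analysis covers demography and the primary objective, not sample collection. Its trigger counts subjects with serological results, although Protocol Table 5 lists no serology assay, and it relies on a Total effective cohort that SAP 5 does not define. SAP 6.1.1 gives the number excluded from ATP, but the text does not promise a split by centre or reason.

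**The case against.** Several points on the other side stand.

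- A reader might infer that any child whose samples were lost inflates the percentage. The table counts samples taken. Dropping a child whose BAL was taken but gave no result leaves the figure unchanged or slightly lower. Only children with no BAL taken and no swab result push it up.
- A reader might infer that these children vanish from the report. They do not: SAP 6.1.1 counts them among the ATP exclusions, and dividing the primary table's denominator by the number enrolled comes close to the overall yield. SAP 8.1 also places individual data in the final report. What the text does not promise is the split by centre and reason.
- A reader might infer that BAL and swab are always lost together. Protocol 3.1 says only that swabbing during sedation adds no discomfort or risk. It does not say the swab is skipped when BAL fails. A failed BAL with a swab result can stay in ATP and show in the table, and the single Day 0 visit suggests a short window for cancellation.
- The ATP rule cannot be wholly literal, since the screened and excluded counts in SAP 6.1.1 cannot be produced on ATP. One could argue that 6.1.7 was meant as disposition output too. But the only stated rule points to ATP, and nothing in 6.1.7 overrides it.
- The table templates annexed to the SAP and the form defining the elimination codes are not in the supplied text and might settle the matter. The form could also cut the other way: if a missing BAL counts as non-compliance with procedures, swab-only children leave ATP as well and the BAL figure is 100% by construction.

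**Conclusion.** The point holds as a minor reporting defect. Under the stated rules, the sample-collection table excludes enrolled children with neither result, overall and by centre. The BAL percentage is biased upward if at least one such child had no BAL taken and such children lacked BAL more often than enrolled children overall. Otherwise the effect is nil or marginally downward: 0 to −0.4 points in the cases worked.

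The actual size cannot be derived, because the documents give no missing-sample rate. For an assumed 3 to 15 of 150 children with neither sample taken, and no other child lacking BAL, the overstatement is 2.0 to 10.0 points.

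A reader might go further and infer that the primary proportions are biased by this table. The documents do not support that: SAP 6.2 sets their denominator separately, as children tested with a BAL result, so no primary estimate or interval changes. What is weakened is the reader's ability to see, centre by centre, how many enrolled children contributed to those estimates.

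**What to change.** In SAP 6.1.7, state that the BAL and swab percentages are computed on the Total cohort (all enrolled subjects), overall and by centre. For each sample type give three rows: not taken; taken without result; result available. In SAP 6, except subject disposition (6.1.1) and sample collection (6.1.7) from the ATP rule; 6.1.1 needs that exception in any case.

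The cost is about two sentences and one changed denominator. No new data collection should be needed: Protocol Table 3 already has sample collection documented in each child's eCRF, and laboratory results go to the study database. The downside is that reported completeness may look slightly less favourable.

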6.2. Analysis of primary objective

The primary analysis will be based on the ATP cohort. If the percentage of subjects from the Total effective cohort with serological results excluded from the ATP cohort is more than 5%, a second analysis based on the Total effective cohort will be performed to support the ATP analysis.

The proportions and associated exact 2-sided 95% confidence intervals (CI) of *H. influenzae*, *S. pneumoniae*, *M. catarrhalis* and other bacteria confirmed by culture in BAL samples (*H. influenzae*, *S. pneumoniae* and *M. catarrhalis* confirmed by bacterial load >10⁴ cfu/mL if present alone or 10⁵ cfu/mL if present as co-infection) will be computed and presented for all study subjects.

The denominators will be the number of tested subjects with BAL sample results available.

6.3. Analysis of secondary objectives

All tables related to secondary objectives 1 to 8 will be presented overall as well as by age class, gender, pneumococcal vaccination status. The age will be grouped into the following classes 6-11, 12-23, 24-35, 36-47, 48-59 and 60-71 months; however, if there are too few subjects in any of the categories, the following classification will be used of 6-23, 24-47, 48-71 months instead.

In a hospital setting and among subjects with suspected chronic LRTIs:

- 1) To describe the bacterial load of *H. influenzae*, *S. pneumoniae* and *M. catarrhalis* detected by quantitative culture and by molecular techniques (PCR) in the BAL fluid.

The distribution (with number of non-missing observations, geometric mean, standard deviation, median, minimum and maximum and number of missing observations) of the bacterial load of *H. influenzae*, *S. pneumoniae*, *M. catarrhalis* in the BAL fluid will be described according to the testing method (culture and PCR).

- 2) To describe the presence of other bacterial pathogens detected by qualitative culture in the BAL fluid.

The presence (number and percentage) of other bacterial isolates detected in BAL fluid will be presented in frequency tables.

- 3) To describe the bacterial load of *H. influenzae*, *S. pneumoniae* and *M. catarrhalis* detected by quantitative culture and by molecular techniques (PCR) in the nasopharyngeal swab samples.

The distribution (with number of non-missing observations, geometric mean, standard deviation, median, minimum and maximum and number of missing observations) of the bacterial load of *H. influenzae*, *S. pneumoniae*, *M. catarrhalis* in the nasopharyngeal swab samples will be described according to the testing method (culture and PCR).

- 4) To describe the presence of other bacterial pathogens detected by qualitative culture in the nasopharyngeal swab samples.

The presence (number and percentage) of other bacterial isolates detected in the nasopharyngeal swab samples will be presented in frequency tables.

- 5) To describe colonisation of the upper airways by characterising *H. influenzae*, *S. pneumoniae*, *M. catarrhalis* and other pathogens in nasopharyngeal swab samples.

Statistical Analysis Plan

Study alias & e-track number(s): EPI-STREP-064 BOD ES (115813)

The occurrence of *H. influenzae*, *S. pneumoniae*, *M. catarrhalis* and other pathogens detected by culture in the nasopharyngeal swab samples will be presented:

The proportions and associated exact 2-sided 95% confidence intervals (CI) of *H. influenzae*, *S. pneumoniae*, *M. catarrhalis* and other pathogens confirmed by culture in the nasopharyngeal swab samples (*H. influenzae*, *S. pneumoniae* and *M. catarrhalis* confirmed by bacterial load $>10^4$ cfu/mL if present alone or 10^5 cfu/mL if present as co-infection) will be computed and presented for all study subjects.

The denominators will be the number of tested subjects with nasopharyngeal swab samples results available.

- 6) To determine the serotypes of *H. influenzae* and *S. pneumoniae* identified from BAL fluid and nasopharyngeal swab samples

The serotype distribution (number and percentage) of *H. influenzae* and *S. pneumoniae* isolates detected in BAL fluid will be presented in frequency tables.

The serotype distribution (number and percentage) of *H. influenzae* and *S. pneumoniae* isolates detected in nasopharyngeal samples will be presented in frequency tables.

- 7) To determine the antibiotic susceptibility profile for *H. influenzae*, *S. pneumoniae* and *M. catarrhalis* identified from BAL fluid samples.

For the antibiotic susceptibility, *H. influenzae*, *S. pneumoniae* and *M. catarrhalis* isolates (detected by culture of BAL fluid and nasopharyngeal swab) will be classified as susceptible, intermediate or resistant (following Clinical and Laboratory Standards Institute guidelines [CLSI, 2015]) see Table 2 and Table 3 below) and will be tabulated by bacterial pathogen and antimicrobial agent.

The percentage of subjects for whom antibiotic resistance test was performed and the results of the resistance test will be tabulated (Antibiotic sensitivity on BAL samples include penicillin, erythromycin, azithromycin, tetracycline, levofloxacin, trimethoprim/ sulfamethoxazole, amoxicillin/ clavulanate; and additionally a beta-lactamase test for *H. influenzae* and *M. catarrhalis*).

The ranges for antimicrobial susceptibility for *S. pneumoniae* are the following:

Table 2 MIC ranges for antimicrobial susceptibility for *S. pneumoniae*

	Susceptible (S) ($\mu\text{g/mL}$)	Intermediate (I) ($\mu\text{g/mL}$)	Resistant (R) ($\mu\text{g/mL}$)
Penicilin	≤ 0.06	0.12 – 1.00	≥ 2.0

Statistical Analysis Plan

Study alias & e-track number(s): EPI-STREP-064 BOD ES (115813)

Amoxicillin / clavulanate	$\leq 2/1$	4/2	$\geq 8/4$
Erythromycin	≤ 0.25	0.5	≥ 1
Azithromycin	≤ 0.5	1	≥ 2
Tetracycline	≤ 1	2	≥ 4
Levofloxacin	≤ 2	4	≥ 8
Trimethoprim / sulfamethoxazole	$\leq 0.5/9.5$	1/19 – 2/38	$\geq 4/76$

The ranges for antimicrobial susceptibility for *H. influenzae* and *M. catarrhalis* are the following:

Table 3 MIC ranges for antimicrobial susceptibility for *H. influenzae* and *M. catarrhalis*

	Susceptible (S) ($\mu\text{g/mL}$)	Intermediate (I) ($\mu\text{g/mL}$)	Resistant (R) ($\mu\text{g/mL}$)
Penicilin	No CLSI standard – MIC values will be presented		
Amoxicillin / clavulanate	$\leq 4/2$	n.a.	$\geq 8/4$
Beta-lactamase (Nitrocefin)	Positive/Negative		
Erythromycin	No CLSI standard – MIC values will be presented		
Azithromycin	≤ 4	Non-susceptible (NS)	
Tetracycline	≤ 2	4	≥ 8
Levofloxacin	≤ 2	Non-susceptible (NS)	
Trimethoprim / sulfamethoxazole	$\leq 0.5/9.5$	1/19 – 2/38	$\geq 4/76$

8) To describe, according to microbiological results observed:

- Age, gender, weight, height and BMI categories
- Clinical symptoms and radiological evidence
- Pneumococcal conjugate vaccine, *H. influenzae* type b vaccine and influenza vaccine status
- Medical history and co-morbidities

Study alias & e-track number(s): EPI-STREP-064 BOD ES (115813)

- Information on feeding and day care practice, environmental exposure and smoking environment
- History of antibiotic use in the past six months as well as other treatments for chronic lower respiratory disease
- Laboratory results [including white blood cell counts, C-Reactive Protein (CRP) level and erythrocyte sedimentation rate, if available].

The demography characteristics (age, gender, weight in kg, height in cm and BMI categories), clinical symptoms and radiological evidence, Pneumococcal conjugate vaccine history status, *H. influenzae* type b vaccine history status and influenza vaccine history status, Medical history, Information on feeding and day care practice, environmental exposure and smoking environment, History of antibiotic use in the past six months as well as other treatments for chronic lower respiratory disease and Laboratory results will be presented by microbiological results of (*S. pneumoniae* positive/negative, *H. influenzae* positive/negative and *M. catarrhalis* positive/negative, co-infection or not co-infection), and by type of sample used (BAL or nasopharyngeal sample) (Details see section 6.1).

